10.4. Discussion of Study Design, Including the Choice of Control Groups

This is an exploratory study to assess the safety and treatment effect of different injection techniques of CCH for the treatment of EFP. The study will also explore the use of 3-D photography in assessing outcomes in EFP. No control groups will be employed.

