11. SELECTION AND WITHDRAWAL OF SUBJECTS

11.1. Subject Inclusion Criteria

No subject will be assigned to treatment until all eligibility criteria have been satisfied. To qualify for the study a subject must:

1. Be able to provide voluntary written informed consent prior to the initiation of any study-specific procedures per the policy of the governing Institutional Review Board (IRB)/Independent Ethics Committee (IEC).
2. Be female and at least 18 years of age at the time of consent.
3. Have evidence of cellulite in 2 bilateral treatment areas (defined as right and left buttocks OR right and left posterolateral thighs) as assessed by the Investigator at the Screening visit, and fulfills the following requirements:
 - a. has a score of 2 (mild), 3 (moderate) or 4 (severe) as reported by the Investigator (CR-PCSS) in 2 treatment areas (two thighs or two buttocks) at the Screening Visit.
 - b. has at least 2 dimples from each treatment area that:
 - are isolated and separated by at least 5 cm from any other dimples.
 - score 2 or 3 on the Hexsel depression scale.
 - have dimple width: length ratio ≥ 0.5 .
4. Be willing to apply sunscreen to the dosing areas before each exposure to the sun while participating in the study (ie, screening through end of study).
5. Be judged to be in good health, based upon the results of a medical history, physical examination, and laboratory profile at screening.
6. Have a negative serum pregnancy test at the Screening Visit and negative urine pregnancy at Day 1 (before injection of study drug), be using an effective contraception method (eg, abstinence, intrauterine device, hormonal [estrogen/progestin] contraceptives, or double barrier control) for at least 1 menstrual cycle prior to study enrollment and through Day 71 ; or be menopausal defined as at least 12 months of amenorrhea in the absence of other biological or physiological causes (as determined by the Investigator), or be postmenopausal for at least 1 year, or be surgically sterile (hysterectomy, bilateral oophorectomy, bilateral tubal ligation).
7. Be willing and able to comply with all protocol required study visits and assessments.

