### 3.11. Hexsel Depression Depth Scale

The Hexsel Cellulite Severity Scale (Hexsel CSS) is a photometric scale that looks at 5 key morphologic features of cellulite (2,3):

- A - number of evident depressions
- B - depth of depressions
- C - morphological appearance of skin surface alterations
- D - laxity, flaccidity or sagging of skin, and
- E - current classification scale based on medical literature

Each of these features is evaluated on a 4-point scale from a low of 0 to a high of 3. For this study, only “B - depth of depressions” will be assessed.

The investigator or qualified designee will use the Hexsel CSS (B) depth of depressions to assess the severity of EFP in each buttock or each thigh. The assessment will be made while the subject is in the standing position with relaxed gluteus muscles at the following visits:

- Screening visit
- Days 22, 43, and 71( EOS/ Early termination)

The labels and descriptions associated with each level of depth of depression of Hexsel CSS (B) are shown in Table 6 below.

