Baseline for Hexsel Depression Depth Scale	The investigator assessment performed at Screening for each treatment area will be considered as Baseline.
Duration of Exposure at Each Visit	Date/Time of Last Injection – Date/Time of First Injection
Duration of AE	AE end date – AE start date + 1
AE Onset Day	AE start date - Date of first injection + 1

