#### **7.7.3. Change from Baseline in Dimple Depth Depression by Hexsel CSS (B)**

The change from baseline in the Hexsel CSS (B) depression depth scale for each treatment area at Days 22, 43, and 71 will be analyzed and summarized as described in Section 7.7.1.1.

In addition, a shift table of Hexsel CSS (B) depression depth evaluation at baseline and post baseline study visit/day will be presented using counts and percentages.

A listing of Hexsel CSS (B) values will be provided.

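### The Screening visit supplies both the Hexsel entry scores and the Hexsel baseline, so within-arm Hexsel change may include regression to the mean that this uncontrolled study cannot separate out

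*SAP*

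**What the plan says.** **Entry.** Protocol 11.1 (repeated in SAP 3.2) judges cellulite "as assessed by the Investigator at the Screening visit, and fulfills the following requirements". One requirement is that the subject "has at least 2 dimples from each treatment area that", among other things, "score 2 or 3 on the Hexsel depression scale". The cut is therefore applied to dimples, at Screening.

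**Baseline.** SAP Table 12 defines the Hexsel baseline: "The investigator assessment performed at Screening for each treatment area will be considered as Baseline". SAP 3.11 says the scale is used "to assess the severity of EFP in each buttock or each thigh", so the analysed score belongs to the area, not to a dimple.

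**Timing.** Both schedules of events, and SAP 3.11 and 4.5.3, place Hexsel at Screening and Days 22, 43 and 71. Day 1 has none. Screening may be up to 21 days before Day 1.

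**Analysis.** SAP 7.7.3 analyses "The change from baseline in the Hexsel CSS (B) depression depth scale for each treatment area at Days 22, 43, and 71" with the mixed model of 7.7.1.1 (arm, visit and their interaction, with 95% confidence intervals) and adds a shift table. SAP 6.2 plans no covariate adjustment.

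**Comparator and rater.** Protocol 10.4: "No control groups will be employed". Under Protocol 12.4 the study is open-label with sequential assignment. The Hexsel rater is the investigator or a qualified designee.

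**The concern.** When subjects are admitted because a noisy score is high, and a score from the same sitting serves as baseline, some of the later fall is rating error washing out. An untreated group would show how much; this study has none. A second rating before dosing would also show it, and none is scheduled.

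At stake is how the within-arm Hexsel results are read. The primary objective is to assess treatment effects under different techniques, so a negative mean change, an interval excluding zero, or a shift table with more improvement than worsening will naturally be taken as effect. Neither document mentions regression to the mean.

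The study does have a Day 1 baseline elsewhere: the 3-D dimple measurements are compared with the Day 1 pre-marking image (SAP 3.9 and 7.7.2).

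**Working it through.** **No figure of the plan's own to reproduce.** Protocol 17.1 reports no sample size estimation, and neither document gives a Hexsel standard deviation, effect or reliability. The only count is the allocation: 6 subjects × 5 arms × 2 regions = 60, as stated.

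**Inputs from the documents:** scale 0 to 3; entry cut of 2 or more on at least 2 dimples per area; baseline an area rating from the same visit; no adjustment; no control group.

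**Assumptions:**
- Test-retest reliability r, mainly 0.8, with 0.6 to 0.9 as the range.
- Scores of 0/1/2/3 before selection in 10/30/40/20%.
- No true change.
- Dimples and area share one true severity, and follow-up rating error is independent of Screening.

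**Model.** Latent rating = true severity (variance r) + error (variance 1 − r), cut at the normal quantiles for 10%, 40% and 80%. A fraction f of the Screening error variance is common to the dimple and area ratings; the rest is independent. Subjects are kept if two dimple ratings are both 2 or more. Bias = mean of (follow-up area score − Screening area score) among those kept. A negative value is apparent improvement.

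| Share of error in common (f) | Spurious improvement, r = 0.8 | r = 0.6 |
|---|---|---|
| none | 0.00 | 0.00 |
| half | 0.07 | 0.15 |
| all | 0.18 | 0.30 |

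**Worst case in more detail.** Sharing all the error is the same as letting one score be both gate and baseline. For the 10/30/40/20% mix the spurious improvement is then 0.12, 0.18, 0.24 and 0.30 points at r = 0.9, 0.8, 0.7 and 0.6. At r = 0.8, about 28% of areas improve by at least one grade and 11% worsen, with nothing having changed. With other mixes (25/25/25/25% and 5/20/45/30%) the worst-case range at r = 0.8 is 0.12 to 0.28.

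**Effect on intervals, worst case only.** Take r = 0.8, the left-right average, an assumed left-right correlation of 0.5 in true severity, and one-sample t intervals. A within-group 95% interval lies wholly on the improvement side in about 8% of cases at n = 6 (one arm in one region) and 41% at n = 30 (one region, all arms), against a nominal 2.5%.

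**Between arms.** The same simulation gives a mean difference of about 0 between two arms under the same entry rule.

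**With a Day 1 baseline.** If Day 1 rating error is independent of Screening and the Day 1 score does not gate entry, the expected change under no effect is 0.00 at every reliability tried. If the Day 1 score also acts as a gate, the single-score model at r = 0.8 leaves about 0.11 points, whichever of the two ratings is the baseline.

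**The case against.** The strongest reply is that the entry cut and the baseline are not the same measurement: one is per dimple, the other per buttock or thigh. This stands, and it governs the size. A reader might take 0.18 points, or 28% improving, as the expected bias; those values need all the rating error to be shared. Zero sharing is equally unproven, since both ratings use the same scale on the same area at the same visit. The rater need not be the same person, because a designee may rate.

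A reader might also infer that Hexsel change is the study's only evidence of effect. It is not. The Likert score comes from a central assessor blinded to arm and visit, and the image measurements start from Day 1. Neither uses the Screening Hexsel score. All five arms share one entry rule, so the bias cancels between them in expectation, although assignment is sequential rather than randomised.

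The Day 1 eligibility re-check (schedule footnote c) could act as a second gate. In the single-score model at reliability 0.8 that would lower the bias from 0.18 to about 0.11, but it would not remove it.

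Two further inferences lack support. Nothing shows investigators rounding scores up so that subjects qualify. Nor does any text show Hexsel being rated after injection on Days 22 and 43. The entries merely lack the pre-dose footnote that photography carries. Volumes per area do differ by arm: 12 × 0.3 = 3.6 mL (I to III), 12 × 1.2 = 14.4 mL (V), 12 × 1.5 = 18.0 mL (IV). However, whether an area is dimple-free must be judged, and sites marked, before dosing, and a dressing is applied afterwards. The timing is unspecified, which is all that can be said.

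Finally, this is an exploratory study with 6 subjects per arm and region. That limits the weight any Hexsel result will carry, but the correction is cheap.

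**Conclusion.** The concern holds for within-arm Hexsel change, for arm-by-visit estimates read as effects, and for the shift table. Entry scores and baseline come from one visit, no other pre-dose rating exists, and the design cannot separate regression to the mean from treatment effect.

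Its size cannot be derived from the documents. At an assumed reliability of 0.8 and a 10/30/40/20% mix it runs from 0.00 to about 0.18 points on a 3-point range, with about 0.07 if half the error is shared. Lower reliability raises the upper end; perfect reliability removes the bias. Comparisons between arms, the Likert endpoint and the 3-D measurements are not affected. The Hexsel timing on Days 22 and 43 is a separate wording gap, not a demonstrated bias.

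**What to change.** - **Day 1 rating.** Schedule an area-level Hexsel (B) rating on Day 1, before arm assignment and study drug, and make it the Hexsel baseline in SAP Table 12. Keep the Screening scores for eligibility.
- **Eligibility re-check.** State that the re-verification under footnote c does not use the new Day 1 area score as a gate. Otherwise the bias partly returns.
- **Reporting.** Present the Screening to Day 1 shift as an estimate of change without treatment.
- **Timing.** Add footnote e to the Hexsel entries at Days 22 and 43, so that those ratings are fixed as pre-dose.
- **If the data are already collected** (SAP version 2.0 is dated 11 February 2019, after the estimated January 2019 completion), state in the report that within-arm Hexsel change may include regression to the mean, and limit Hexsel inference to comparisons between arms.

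The cost is one brief live rating per area at a visit where the dimples are already examined and marked, plus short changes to both schedules and Table 12. The apparent Hexsel improvement will probably be smaller.

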14.5. Reporting Adverse Events and Serious Adverse Events

14.5.1. Reporting Adverse Events

Throughout the study, AEs will be documented on the source document and on the appropriate page of the eCRF whether or not considered treatment-related. This includes any new signs, symptoms, injury or illness, including increased severity of previously existing signs, symptoms, injury, or illness. Conditions existing prior to screening will be recorded as part of the subject's medical history. The Investigator is responsible for assessing the relationship of AEs to the study medication; relationship will be classified as not related, unlikely related, possibly related, or probably related.

All AEs will be collected by the Investigator from the time of signing the informed consent through 28 days after the last dose of study medication; this includes any AEs that are ongoing at the time of completion/termination of the study. All ongoing AEs must be followed until resolution or for 28 days after the subject's last study visit, whichever comes first.

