**6. STATISTICAL METHODS**

**6.1. General Methodology**

All statistical tests, summary tables and data listings will be prepared using SAS version 9.4

All statistical tests of efficacy parameters will be two-sided with a significance level of  $\alpha=0.05$ , unless specified otherwise. Statistical tests will be supported by presenting estimates and 95% confidence intervals (CI) for the respective treatment effects. These estimates and CI will be based on the linear regression model.

Continuous data will be summarized using descriptive statistics. Discrete data will be summarized using frequency counts and percentages. The denominator will be based on the number of subjects in the appropriate population.

For the purpose of display, the summary results will be rounded as follows:

- Minimum and maximum: same number of decimal places as the raw data.
- Mean and Median: one more decimal place than the raw data.
- SD: Two more decimal places than the raw data.
- Percentages will be displayed with one decimal place precision. A zero count will be left blank.
- The standard form of a percentage change variable is 0 decimal place.

For categorical variables with missing values, a category documenting the frequency of missing values will be displayed in the summary tables.

Summary tables, subject listings, graphs and any supportive SAS output will include footnotes that will indicate:

- Date of data extraction
- Date and time of output generation
- SAS program name, including the path, that generated the output

When calculating percentages, the denominator will be based on the number of subjects with non-missing values. If the denominator is expected to change over time, then the denominator used to calculate the percentage will be based on the number of subjects with non-missing values at each visit. Any subject removed from an analysis will be noted at the bottom of the table along with the reason the subject was removed.

Empty summary tables will be presented with a note stating that “No Subjects Met Criteria.”

Subject listings of all data from the eCRFs as well as any derived variables will be presented.

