## **6.4. Handling of Missing Data**

Subjects who discontinue the study prior to or after the initiation of the study drug will not be replaced and available data for these subjects until the point of discontinuation will be summarized.

The missing baseline assessment will not be imputed.

For categorical variables with missing values, a category documenting the frequency of missing values will be displayed in the summary tables.

Subjects who discontinue early will be encouraged to have all Day 71 procedures and assessments completed at an early termination visit.

There will be no imputation of missing values for safety data, however missing relationship between AE and study drug will be considered as related to study drug following worst case principle. Missing severity of an AE will be summarized as a severe AE.

Immunogenicity samples with a positive titer value will undergo a log transformation for analyses. Samples with titer level less than 1 will be assigned or imputed as a log transformed titer of zero (0) for analyses.

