### **6.4.1. Imputation of Partial Dates**

#### **6.4.1.1. TEAE Status for Completely Unknown Start Date**

The following rules will apply in cases where start date of an AE is completely unknown:

- If the AE onset date is unknown and the end date is after first injection on Day 1 or ongoing, then the AE will be considered a TEAE.
- If the AE onset date is unknown and the end date is before first injection on Day 1, then the AE will not be considered a TEAE.
- If both the start and end dates are unknown (or end date is ongoing), then the AE will be considered a TEAE, following the worst-case principle.

If the AE onset date is partly present and month/year is prior to the first injection date then the AE will not be considered a TEAE.

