### **7.8.2. Adverse Events**

All AE summary tables will include only TEAEs, unless otherwise specified.

AEs will be summarized by SOC and PT. A subject will only be counted once per SOC and PT.

For AEs by severity grade (mild, moderate, severe), if a subject has multiple events occurring in the same SOC or same PT, then the event with the maximum intensity (ie, severe) will be counted.

For AEs by relationship to study drug, if a subject has multiple events occurring in the same SOC or same PT, the event with the highest association (ie, related) to study drug will be summarized.

AEs will be presented in decreasing order of the incidences at SOC level and within each SOC, in decreasing order of the incidences at the PT level.

An overall summary of AE and AE related to study drug will be presented and will include:

- Total number of TEAEs reported
- Total number of TEAEs reported by severity
- Total number of AEs of special interest
- Subjects with any TEAE
- Subjects with any special interest AE
- Subjects with any serious TEAE
- Subjects with any severe TEAE

- Subjects with no severe TEAEs, but at least one moderate TEAE
- Subjects with no severe TEAEs, but at least one mild TEAE
- Subjects with any TEAEs leading to drug interruption/withdrawn
- Subjects with any TEAEs leading to study discontinuation
- Subjects with any TEAEs resulting in death

The following summary tables will be presented by SOC and PT:

- All TEAEs
- TEAEs by severity
- TEAEs by relationship to study drug
- All non-study drug related TEAEs
- All study drug related TEAEs
- Study drug related TEAEs by severity
- Serious TEAEs
- Serious study drug related TEAEs
- Duration of study drug related TEAEs (<14 days, 14 – 21 days and >21 days)
- TEAEs leading to drug interruption/withdrawn
- Study drug related TEAEs leading to drug interruption/withdrawn
- TEAEs leading to study discontinuation
- Study drug related TEAE leading to study discontinuation
- TEAEs resulting in death
- Study drug related TEAEs resulting in death
- AEs of special interest

Serious and most common non-serious TEAE by order of frequency (Most frequent, 2nd most frequent, and 3rd most frequent) will be summarized by PT. Most common non-serious AEs are any preferred term that at least 5% of the subjects reported at least once.

The following listings will be presented by subject:

- All AEs
- Serious AEs
- AEs resulting in drug interruption/withdrawn

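### Drug-related adverse events still ongoing at last contact get no duration under the SAP, so they cannot enter the >21 days row even when follow-up shows that they lasted longer

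*SAP*

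**What the plan says.** SAP 7.8.2 lists, among the tables by system organ class and preferred term, "Duration of study drug related TEAEs (<14 days, 14 – 21 days and >21 days"). SAP Table 12 supplies the derivation: "AE end date – AE start date + 1". It has no second line for an event without an end date.

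SAP 6.4 states "There will be no imputation of missing values for safety data", then makes two exceptions: missing relationship counts as related and missing severity counts as severe. The same section adds: "For categorical variables with missing values, a category documenting the frequency of missing values will be displayed in the summary tables". On percentages, SAP 6.1 says "When calculating percentages, the denominator will be based on the number of subjects with non-missing values", although it also says that the denominator rests on the number of subjects in the appropriate population.

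The SAP knows that an event can be ongoing. SAP 6.4.1.1 includes the case "If the AE onset date is unknown and the end date is after first injection on Day 1 or ongoing", but uses it only to decide whether the event is treatment-emergent. Table 12 also defines Last Date in Study, which is not linked to event duration.

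Protocol 14.5.1 collects events "through 28 days after the last dose of study medication" and adds: "All ongoing AEs must be followed until resolution or for 28 days after the subject's last study visit, whichever comes first".

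**The concern.** Short events resolve and get a duration. Events that do not resolve during follow-up get none, and these are mostly the longest. The gap therefore works in one direction: the >21 days row loses events that belong in it, and the arm with the most persistent reactions loses most.

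The row has a practical meaning. Treatments are 21 days apart, and Protocol 8.4 relies on the observation that most events in earlier studies resolved before the next treatment. The >21 days class shows whether that holds for each injection technique, and safety by technique is the secondary objective.

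The gap also departs from the SAP's own habit. Missing severity, missing relationship and wholly unknown event dates are all resolved in the unfavourable direction. Only for duration does incomplete information make the result look better.

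**Working it through.** The plan states no figure on this point to reproduce. The check is a day count with the SAP's own formula, using the last follow-up date as a lower bound for the missing end date.

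**Inputs**
- Injections on Days 1, 22 and 43; third treatment visit Day 43 ± 2; final visit Day 71 ± 3 (Protocol section 5).
- New events collected to 28 days after the last dose; ongoing events followed to 28 days after the last visit (Protocol 14.5.1).
- 6 subjects per region per arm, so 12 per arm (SAP 3.1).

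**Minimum observed duration of an event still ongoing when follow-up ends**

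Let V be the day of the last dose and L the day of the last visit. The latest onset collected is V + 28 and follow-up ends on L + 28. The minimum is (L + 28) − (V + 28) + 1 = L − V + 1.
- Nominal schedule: 71 − 43 + 1 = 29 days.
- Worst windows (dose on Day 45, final visit on Day 68): 68 − 45 + 1 = 24 days.

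Both exceed 21. In a subject who receives the third dose, reaches the final visit and is followed per protocol, every related event still ongoing at the end is known to have lasted more than 21 days. If the last dose was earlier, L − V is larger and so is the minimum.

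**Where this fails**
- Last visit is a dosing visit (L = V). Onset on V + 7 gives 28 − 7 + 1 = 22 days; onset on V + 8 gives 21. Ongoing events that start from V + 8 (Day 51 when V is Day 43) are observed for 21 days or less.
- Subjects lost to follow-up: the observed time may be shorter still.

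**If only Last Date in Study is available**

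For a completer this is Day 71. Onset on Day 50 gives 71 − 50 + 1 = 22 days; onset on Day 51 gives 21. Ongoing events with onset up to Day 50 can still be placed in >21 days.

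**Effect on the row (illustration; the counts are assumed, not taken from the documents)**

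Take 12 subjects in an arm, all with a related event. Two have events that resolved after more than 21 days, and 0 to 3 have an event that is ongoing and known to exceed 21 days.

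| Ongoing | As written, non-missing denominator | As written, denominator 12 | Ongoing counted as >21 days |
|---|---|---|---|
| 0 | 2/12 = 16.7% | 16.7% | 2/12 = 16.7% |
| 1 | 2/11 = 18.2% | 16.7% | 3/12 = 25.0% |
| 2 | 2/10 = 20.0% | 16.7% | 4/12 = 33.3% |
| 3 | 2/9 = 22.2% | 16.7% | 5/12 = 41.7% |

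On a fixed denominator, one subject is worth 1/12 = 8.3 points in an arm and 1/6 = 16.7 points in an arm-by-region cell.

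**The case against.** The strongest reply is that nothing is lost. A missing category must be displayed, every adverse event is listed by subject, and with about 60 subjects the unresolved events can be found. A reader might infer that these events vanish from the table; the documents do not support that. What stands is the labelling: a duration known to exceed 21 days is shown as unknown, and the >21 days row remains too low.

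Second, placing an event known to be ongoing beyond 21 days in the top class could be called classification rather than imputation, and the table shells in SAP Module 2, which are not among the documents, may hold an ongoing row. Both are possible. But the only derivation given yields no value for such an event, and a shell row would still need a rule to fill it.

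Third, a reader might infer that every unresolved event is known to exceed 21 days. That is not so for subjects lost to follow-up or for some who stop early, as the day count shows.

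Fourth, the numbers may be small. Protocol 8.4 says that most events resolved before the next treatment. The Phase 2b rates in Protocol 8.3 (nodule 14.3%, induration 5.8%; about 0.143 × 12 = 1.7 and 0.058 × 12 = 0.7 subjects per arm) are incidences and say nothing about persistence. This limits the likely size but does not remove the direction.

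Finally, this is one descriptive table with no test attached. The tables by severity, by relationship and of special-interest events are untouched, as are the efficacy analyses. That is correct and keeps the point modest.

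**Conclusion.** The point holds in a limited form. As written, a drug-related event that is ongoing at last contact cannot be counted as >21 days. For subjects who reach Day 71 and are followed as the protocol requires, it is known to belong there, with at least 29 days observed nominally and 24 at the worst windows. The row is biased downwards, and more so in arms with more persistent reactions.

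The size cannot be stated, because the share of events unresolved at last contact is not given. The percentages in the table above rest on assumed counts and should not be read as estimates.

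The conclusion assumes that the post-visit follow-up is carried out and that no rule in the unseen shells fills the gap. It is a correction worth making to one safety table, not a threat to the trial's main results.

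**What to change.** 1. In SAP Table 12, add for an event with no end date: minimum duration = date last known ongoing − start date + 1. If no later contact date is recorded, use Last Date in Study.
2. In the SAP 7.8.2 duration table, count the event in >21 days when this minimum exceeds 21. Show the remainder in a row labelled as ongoing with 21 days or less observed.
3. State that subjects with ongoing events stay in the denominator of this table.

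This uses an observed lower bound, so it does not assume that any event is long.

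The cost is a few sentences in the SAP and one extra derivation, and the >21 days figures become slightly less favourable. The documents do not name a recorded field for the date an event was last known to be ongoing. If none exists, the fallback date still works, but a completer's ongoing events with onset after Day 50 (final visit on Day 71) would fall in the extra row. No change to visits or treatment is needed.
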